## 8.2. Adverse Events Grading

All AEs (laboratory and clinical symptoms) will be graded for severity and assessed for relationship to study product (see definitions). AEs will be graded initially by the study team on-site, typically the nurse and/or study physician, and final grading of AEs will occur in consultation with [name]. AEs characterized as intermittent require documentation of onset and duration of each episode. The start and stop date of each reported AE will be recorded on the appropriate data collection form. Changes in the severity of an AE will be documented to allow an assessment of the duration of the event at each level of intensity.

### 8.2.1. Severity of Event:

Severity will be determined following the definitions set forth in the standardized grading of adverse events (NIH Division of AIDS Adult and Pediatric Toxicity Tables, November 2014, version 2.0; see: [https://rsc.tech-res.com/docs/default-source/safety/daids\\_ae\\_grading\\_table\\_v2\\_nov2014.pdf](https://rsc.tech-res.com/docs/default-source/safety/daids_ae_grading_table_v2_nov2014.pdf)). Use of these standardized guidelines will allow for uniform reporting. The grades are defined as follows:

- Grade 1: Mild AE
- Grade 2: Moderate AE
- Grade 3: Severe AE
- Grade 4: Potentially Life-threatening AE
- Grade 5: Death

Changes in the severity of an AE should be documented to allow for assessment of the duration of the event at each level of intensity to be performed. Adverse events characterized as intermittent require documentation of onset and duration of each episode.

#### **8.2.2. Relationship to Study Product:**

The assessment of the relationship of an AE to the administration of study product is made only by those with the training and authority to make a diagnosis based on all available information at the time of the completion of the case record form. Whether the AE is related or not, is not a factor in determining what is or is not reported in this trial. If there is any doubt as to whether a clinical observation is an AE, the event should be reported. In a clinical trial, the study product must always be suspect. To help assess, the following general guidelines are used:

- Related – There is a reasonable possibility that the study product caused the AE. Reasonable possibility means that there is evidence to suggest a causal relationship between the study product and the AE.
- Not Related – There is not a reasonable possibility that the administration of the study product caused the event.

The physician-investigators will use clinical judgment to determine the relationship with more specific objective criteria. Alternative causes, such as natural history of the underlying diseases, concomitant therapy, other risk factors, and the temporal relationship of the event to the investigational product will be considered and investigated. The physician-investigators will also consult the drug information and the DSMB as needed in the determination of their assessment.

There may be situations when an SAE has occurred, and the investigator has minimal information to include in the initial report. However, it is very important that the investigator always make an assessment of causality for every event prior to transmission of the SAE report to CSU, Yale, IRSS and DMID. The investigator may change his/her opinion of causality in light of follow-up information, amending the SAE case report form accordingly.

#### **8.3. Management and Reporting of AEs**

AE monitoring will occur both actively and passively. All AE will be graded and analyzed by seriousness, intensity and causality. AE monitoring in this study is crucial to properly weigh the potential benefits vs. potential risks of the study.

- In the entire enrolled populace, passive monitoring of AEs will occur through spontaneous reporting of events to the study clinical team, and recorded on CRFs. AEs will be recorded from the entire

---

enrolled populace, regardless if they were treated with ivermectin/placebo or not eligible to take the intervention. AEs will also be actively monitored on the days of distribution of ivermectin/placebo through direct questioning of AEs and recording on CRFs by study nurses. AE will be recorded over the intervention period occurring during 1st and 2nd rainy seasons. More specifically, AEs will be recorded from the start of the first MDA of each rainy season to 1 month after the last MDA of that season.

- For those children enrolled in the active case detection cohort, where children are visited weekly to assess for malaria incidence, active monitoring of AEs will occur through direct questioning of AEs by the study team. Additionally, passive monitoring of AEs will occur by participants spontaneously reporting directly to the nurses when the nurses are in the villages performing active case detection of malaria in the child cohort, or spontaneously reporting indirectly to the nurses via communication through the village community health worker (who will then communicate the AE directly to the nurse or field physician).
- For women that become pregnant during the intervention period, from the time of 1st intervention to 1 month after the last intervention for each rainy season, monitoring for birth outcomes will be conducted.

Participants who develop common AEs that possibly were a consequence of ivermectin treatment will be identified at follow-up visits and treated by the study nurses according to WHO guidelines for treating common AEs that occur from MDAs (see appendix B) as well as standard approaches in Burkina Faso. All adverse events will be noted in the participant's CRF.

In the case of mild AE, no further action will be taken by study staff except in the case of vomiting, in which case the study medication may need to be re-administered. AEs will be followed until resolution even if this extends beyond the study-reporting period. Resolution of an AE is defined as the return to pretreatment status or stabilization of the condition with the expectation that it will remain chronic. These will be collated from CRFs by the field physician and study data managers in the 4th week following each IVM MDA and reported to the PIs prior to the administration of the next IVM MDA.

### 8.3.1. **Serious Adverse Events**

SAEs will be:

- Assessed for severity and relationship to study product and alternate etiology.
- Recorded on the appropriate SAE data collection form.

---

- Followed through resolution.
- Reviewed and evaluated by the DSMB (periodic review unless related), DMID, and the IRB.

In the case of any SAE, subjects will be referred to the district hospital for management. Transportation to the hospital will be provided. All hospitalized participants will undergo record review to identify potential adverse consequences of study participation.

At any time after protocol follow up period or completion of this study, if the site principal investigator or appropriate sub-investigator becomes aware of an SAE that is suspected to be related to study product, the site principal investigator or appropriate sub-investigator will report the event to the DMID Pharmacovigilance Group.

All SAEs will be reported to the DMID (see below), to the Physician-PI ([name]) and to the in-country investigator ([name]), or their assigned representatives, within 24 hours of the nursing staff becoming aware of it via mobile phone or electronically. The SAE form in the CRF will ask for nature of event, date of onset, severity, corrective therapies given, outcome and causality (i.e. unrelated, unlikely, possible, probably, definitely). The responsible study clinician should ultimately assign the causality of the event.

AEs that are serious or unexpected and are at least 'possibly related' to the intervention require expedited reporting within 24 hours of nurse becoming aware of it, and reporting within 24 hours to the sponsor by the country investigator or assigned representative becoming aware of it (e-mail notification); i.e. this will be a maximum of 48 hours after the field nurse becomes aware of it (including the 24 hours required for the field staff to report to the country investigator / representative). The DMID will report all SAEs to the DSMB. Additional information will be sent within 14 additional days (full SAE report) if the reaction had not resolved at the time of e-mail notification.

**Table 5: Reporting of Adverse Events**

Institution	Type of Adverse Events	When to Report

 
• Yale-HIC
 
• CSU IRB
 
• IRSS/Centre Muraz
 
	
 
• Related and Not Related to participation in the research AND Serious OR Unexpected (in terms of nature, specificity, severity, or frequency)
 
	
 
• Within 5 days of awareness
 
• Related Events not meeting prompt reporting requirements are reportable in summary form at time of continuing review
 

DMID Pharmacovigilance Group¥	
 
• All Serious Adverse Events (as defined in 9.1)
 
	
 
• Within 24 hours
 

---	--	---

¥All SAEs must be submitted within 24 hours of site awareness on an SAE form to the DMID pharmacovigilance contractor, at the following address:

### 8.3.2. Reporting of Pregnancy

Pregnancies communicated by any participants to the clinical team, or discovered by the clinical team with the use of screening by urine RDT pregnancy tests prior to each IVM MDA, will be noted on the participant's CRF. The CRF indicator will then be used to identify these participants as not being eligible for receiving the intervention (IVM or placebo). The pregnancy status of these individuals will not be reported to the IRBs, sponsor, or regulatory agencies.

Enrolled women that become pregnant during the intervention period, from the time of 1st intervention to 1 month after the last intervention for each rainy season, monitoring for birth outcomes will be conducted.

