### 3.2.2. Secondary

- AE monitoring will occur both actively and passively. All AE will be graded and analyzed by seriousness, intensity and causality. AE monitoring in this study is crucial to properly weigh the potential benefits vs. potential risks of the study.
- In the entire enrolled populace, passive monitoring of AEs will occur through spontaneous reporting of events to the study clinical team, and recorded on CRFs. AEs will be recorded from the entire enrolled populace, regardless if they were treated with ivermectin/placebo or not eligible to take the intervention. AEs will also be actively monitored on the days of distribution of ivermectin/placebo through direct questioning of AEs and recording on CRFs by study nurses for all participants. AE will be recorded over the intervention period occurring during the 1st and 2nd rainy seasons. More specifically, AEs will be recorded from the start of the first MDA of each rainy season to 1 month after the last MDA of that season.
- For those children enrolled in the active case detection cohort, where children are visited weekly to assess for malaria incidence, active monitoring of AEs will occur through direct questioning of AEs by the study team. Additionally, passive monitoring of AEs will occur by

---

participants spontaneously reporting directly to the nurses when the nurses are in the villages performing active case detection of malaria in the child cohort, or spontaneously reporting indirectly to the nurses via communication through the village community health worker (who will then communicate the AE directly to the nurse or field physician).

- For women that become pregnant during the intervention period, monitoring for birth outcomes will be conducted. Pregnancies will be followed in both arms of the study.
- Entomological indices will provide a first-order mechanistic explanation of the intervention's effect on malaria incidence (the primary outcome): Wild, blood-fed, indoor-aspirated, *Anopheles* will be held in cages and scored for survival rates over time, which will be analyzed across arms. The age structure of captured *Anopheles* will be analyzed over time and analyzed across arms. Captured wild mosquitoes will be dissected and analyzed for sporozoite infection rates over time and analyzed across arms. A cohort of participants' sera immuno-reactivity to an *Anopheles* saliva antigen will be analyzed over the intervention period of each season.

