## 5.2. Subject Exclusion Criteria

Exclusion criteria for participating in the intervention (IVM/placebo MDA):

- Residence outside of the study village
- Height < 90 cm (\*note: if subject becomes ≥90cm over course the trial, this exclusion criteria will no longer be valid in subsequent MDA)
- Current treatment with SP+AQ as part of SMC (restricted to children 3-59 months old) (\*note: if subject discontinuous SP+AQ treatment because they become older than 59 months over course the trial, this exclusion criteria will no longer be valid in subsequent MDA)
- Permanent disability or serious medical illness that prevents or impedes study participation and/or comprehension
- Pregnancy (screened for in women of child-bearing age [ages 12-45] using a pregnancy urine rapid test [e.g. SD Bioline hCG] the week prior to each MDA), as well as older females who have not yet had menopause
- Breast feeding if infant is within 1 week of birth
- Known allergy to ivermectin
- Possibility of *Loa loa* infection as assessed by travel history to Angola, Cameroon, Chad, Central African Republic, Congo, Democratic Republic of Congo, Equatorial Guinea, Ethiopia, Gabon, Nigeria, and Sudan.
- Enrolled in any other active clinical trials

Active case surveillance cohort exclusion criteria:

- Residence outside of the study site
- Permanent disability, serious medical illness that prevents or impedes study participation

---

Additional PK/PD cohort exclusion criteria:

- Concurrent use of drugs known to interfere with CYP3A4 metabolism within the past 14 days. (Section 6.6)
- Hemoglobin < 7g/dL

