### 5.3.3. Reasons for Withdrawal and Discontinuation of Study Product Administration

Participants (or parent/guardians) may voluntarily withdraw their consent/assent at any stage for study participation without penalty or loss of benefits to which they are otherwise entitled.

An investigator may withdraw a subject from receiving the study product for any reason. Follow-up safety evaluations will be conducted, if the subject agrees. If a subject withdraws or is withdrawn prior to completion of the study, the reason for this decision must be recorded in the case report forms (CRFs).

The reasons, might include, but are not limited to the following:

- Screening error resulting in incorrect enrollment (discovery that the subject did not meet the required inclusion/exclusion criteria)
- Withdrawal of assent/consent at any stage or the subject is not willing to continue in the study (or withdrawal of consent by the parent/guardian to keep his or her child enrolled).
- Suspected or confirmed allergic reaction to the study drugs.
- Safety reasons as judged by the investigators or the DSMB after a meeting to review safety.
- Subject no longer meets eligibility criteria (e.g. becomes pregnant)
- Subject becomes noncompliant
- Medical disease or condition, or new clinical finding(s) for which continued participation, in the opinion of the investigator might compromise the safety of the subject, interfere with the subject's successful completion of this study, or interfere with the evaluation of responses
- Subject lost to follow-up
- Determined by a physician's discretion to require additional therapy not indicated in the protocol to ensure subject's health and well-being (or treatment failure, if applicable)

The investigator should be explicit regarding study follow-up (e.g. safety follow-up) that might be carried out despite the fact the subject will not receive further study product. If the subject consents, every attempt will be made to follow all AEs through resolution. The procedures that collect safety data for the purposes of research must be inclusive in the original informed consent or the investigator may seek subsequent informed consent using an IRB/IEC-approved consent form with the revised procedures.

The investigator will inform the subject that already collected data will be retained and analyzed even if the subject withdraws from this study.

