### 8.5. Data and Safety Monitoring Board

Safety oversight will be conducted by a DSMB that is an independent group of experts that monitors subject safety and advises DMID. The DSMB members will be separate and independent of study personnel participating in this trial and should not have scientific, financial or other conflict of interest related to this trial. The DSMB will consist of members with appropriate expertise to contribute to the interpretation of the data from this trial, and include a biostatistician, clinicians and scientists who are knowledgeable about malaria and field-based research in sub-Saharan Africa, and persons knowledgeable in the conduct of clinical trials.

The DSMB will operate under the rules of a DMID-approved charter that will be written at the organizational meeting of the DSMB. Procedures for DSMB reviews/meetings will be defined in the charter. DSMB reports may include enrollment and demographic information, medical history, concomitant medications, physical assessments, clinical laboratory values, dosing compliance, and solicited and unsolicited AE/SAEs. The DSMB will review SAEs on a regular basis and ad hoc during this trial. The DMID Medical Monitor will be responsible for reviewing SAEs in real time.

The DSMB will conduct the following reviews:

- The study's safety data will be analyzed by the DSMB after the interim analyses conducted after the 2nd MDA, and another conducted after the first full season of treatment.
- Ad hoc when a halting rule is met or DMID/DSMB chair may convene an ad hoc meeting if there are immediate concerns regarding observations during the course of this trial.
- Final review meeting: 6 to 8 months after clinical database lock to review the cumulative unblinded safety data for this trial. The data will be provided in a standard summary format. The DSMB may be asked to provide recommendations in response to questions posed by DMID.

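### Protocol section 8.3.2 withholds pregnancy status from the sponsor, IRBs and regulators with no exception for women already given study product, and no planned report counts pregnancies after dosing.

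*Protocol*

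**What the plan says.** Protocol section 8.3.2 covers two routes by which a pregnancy becomes known. One is self-report ("Pregnancies communicated by any participants to the clinical team"). The other is testing: pregnancies "discovered by the clinical team with the use of screening by urine RDT pregnancy tests prior to each IVM MDA". In both cases the pregnancy goes on the CRF, and the flag is used to make the woman ineligible for ivermectin or placebo. The section then states: "The pregnancy status of these individuals will not be reported to the IRBs, sponsor, or regulatory agencies".

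Section 5.2 excludes pregnant women from the drug rounds. Pregnancy is "screened for in women of child-bearing age [ages 12-45] using a pregnancy urine rapid test" in the week before each round, and section 7.2 repeats this. Section 5.3.3 lists becoming pregnant among the reasons for withdrawing study product.

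The second paragraph of 8.3.2 provides birth-outcome monitoring for enrolled women who become pregnant between the first round and one month after the last round of a season. Section 3.2.2 adds: "Pregnancies will be followed in both arms of the study". No recipient or timing for counts of these pregnancies is given.

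On oversight, section 8.5 says "DSMB reports may include enrollment and demographic information, medical history, concomitant medications, physical assessments, clinical laboratory values, dosing compliance", followed by adverse events and serious adverse events. Pregnancies are not in that list. Section 10.3.1 (interim safety review), SAP 2.2.1 (adverse events analysis) and SAP section 3 (planned tables, figures and listings) have no pregnancy item either.

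**The concern.** The protocol treats pregnancy as a safety matter. It excludes pregnant women, says in 2.3.1 that the study will avoid treating them, and in 13.3 requires that participants be told of possible unforeseeable risks to an embryo or fetus. Section 2.3.1 also identifies the trial's greatest potential risk as giving this regimen more often, to more people and to a broader range of ages than in the earlier Kenyan trial.

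The pre-round test is the main safeguard against dosing in pregnancy. A woman who conceives shortly before or after a round may be dosed and test positive only before a later one. Under 8.3.2 her status is withheld from the sponsor, IRBs and regulators exactly as if she had never been dosed.

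At stake is whether anyone overseeing the trial can judge, between rounds, how often the safeguard is passed. Any pregnancy loss or other event that does reach them would arrive without the number of exposed pregnancies it should be set against.

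**Working it through.** The plan states no figure for pregnancies, so there is none to reproduce. The check sets the passages side by side and then illustrates the scale.

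**1. Does the bar reach women already dosed?** There are four rounds per season over two seasons, each preceded by a test (5.2, 7.2). Rounds are monthly, so the tests before rounds 2, 3 and 4 fall about three to four weeks after the previous round. That is 3 × 2 = 6 of the 8 scheduled tests. The test before the first round of season 2 can also find women dosed in season 1. Section 5.3.3 foresees pregnancy arising during participation. Nothing in 8.3.2 separates these women from those never dosed, so the answer is yes.

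**2. Who is barred, and who is not?**

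| Body | Named in the bar? | Other route to pregnancy data |
|---|---|---|
| Sponsor/DMID | Sponsor is named | All serious adverse events within 24 hours (8.3.1, Table 5); right to inspect records (11) |
| IRBs | Yes | Serious or unexpected events within 5 days (Table 5) |
| Regulators | Yes | Right to inspect records (11) |
| DSMB | No | Serious events passed on by DMID (8.3.1); adverse event risk by arm at interim reviews (10.3.1); may request more data (8.5) |

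Each route carries events or permits access. None supplies a routine count of pregnancies after dosing.

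**3. Could the count be produced?** Yes. Pregnancy is on the CRF (8.3.2), as is drug administration (6.5), and dispensing records hold dates and subject numbers (6.4).

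**4. Scale (illustration only).** From the protocol's Treatment Arms table: about 2,500 people per arm, about 75% dosed. Assumptions that are not in the documents: 20–25% of those dosed are women aged 12–45, with 0.10–0.20 conceptions per woman-year.

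- Dosed per arm: 0.75 × 2,500 = 1,875.
- Dosed women aged 12–45: 1,875 × 0.20 = 375 to 1,875 × 0.25 ≈ 469.
- Conceptions = women × yearly rate × fraction of a year.

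Three ways of choosing the window, per arm per season:

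- (a) Every conception from the first round to one month after the fourth (4 months): 375 × 0.10 × 4/12 = 12.5 to 469 × 0.20 × 4/12 ≈ 31.
- (b) Only conceptions in the two weeks before a round, assumed too early for the urine test (4 × 14 = 56 days): 375 × 0.10 × 56/365 ≈ 6 to 469 × 0.20 × 56/365 ≈ 14.
- (c) Only conceptions after the first round that the round 2–4 tests could find, assuming a two-week detection lag (about 2.25 to 2.5 months): 375 × 0.10 × 2.25/12 ≈ 7 to 469 × 0.20 × 2.5/12 ≈ 20.

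The spread is about 6 to 31. These are pregnancies after study product; only the ivermectin arm's share is exposed to ivermectin.

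**The case against.** The strongest reply is that oversight is not blind to pregnancy.

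- **The DSMB is not barred.** Section 8.4 gives it the decision on discontinuing arms. Section 8.5 lets it see unblinded grouped data and request more. The list of report contents is permissive, and 10.3.1 leaves the types of analysis to a charter that is not part of these documents. This stands: for the DSMB the gap is silence, not prohibition.
- **Events still travel.** A congenital anomaly, death or hospitalization is a serious adverse event under 8.1 and reaches DMID, the IRBs and the DSMB. A pregnancy loss recorded as an unexpected adverse event also reaches the IRBs. This stands for events but supplies no denominator. An anomaly would usually be recognised only at birth, often after that season's rounds, and an early loss without hospitalization does not automatically meet the serious criteria.
- **The bar concerns individuals' status.** It does not mention aggregate counts, and interim safety reports go to the IRBs, DMID and DSMB (14.4). This stands in part: an aggregate count is not expressly forbidden, but no passage provides for one.
- **The section does more than stop dosing.** Its second paragraph adds birth-outcome monitoring. This stands; the data are collected, and only their reporting during the rounds is missing.
- **The blind limits what reporting can show.** Sponsor and IRBs could learn of pregnancies after study product, not after ivermectin. This stands and shapes the fix.

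A reader might infer that the bodies able to act can never learn how many pregnancies were exposed to ivermectin. The documents do not support that: the DSMB can both ask and act.

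**Conclusion.** The point holds as a gap in routine reporting. The non-reporting sentence is unqualified and, because tests are repeated, covers women who took study product in an earlier round. No listed DSMB content, interim review item or SAP safety table makes good the missing count. The DSMB would have to think to ask for it.

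It would be a mistake to read the plan as concealing pregnancy harms. Serious events are reported and birth outcomes are monitored.

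The textual finding does not depend on the size estimate. The range of about 6 to 31 per arm per season rests on an assumed share of women, conception rate and detection lag. It shows only that the count is plausibly not trivial. The top of the range includes conceptions that the round 2–4 tests could not find. This should be corrected because the remedy is cheap and concerns safety oversight; it does not bear on the primary efficacy analysis.

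**What to change.** Three changes, none of which touches dosing or eligibility:

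1. In 8.3.2, limit the non-reporting sentence to women found pregnant before any dose of study product.
2. State that a pregnancy found after a dose is reported to the sponsor/DMID and the IRBs by study code and without arm, so that confidentiality and the blind are kept.
3. Add to each DSMB closed report, and to the SAP safety tables, the number of such pregnancies by arm and by round of last dose. The round of last dose separates recent exposure from exposure in a previous season.

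The cost is protocol wording, one row in the DSMB closed report and one in the SAP safety tables, and a small continuing reporting burden. The data are already collected, and study codes already exist under 13.5. If the sentence was written to protect privacy, coded reporting preserves that purpose.
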